14.1.4 Early Subclinical Cardiotoxicity, Fatigue and QoL Endpoints

Each patient will provide baseline testing results after surgery and/or before the start of RT. We will preliminarily assess the correlation between receipt of IMRT and cardiotoxicities as measured by CPET, strain echocardiogram, cardiac blood markers, FMD and QOL questionnaires in 20 patients using Wilcoxon rank sum test (for continuous measures) and Fisher exact test (for categorical measures). Among the 20 patients whose data will be counted towards the analysis of these exploratory endpoints, 10 of them are in the control group of patients who do not receive IMRT (Group 2B). The data from these 10 patients in the control arm will only be utilized to study the exploratory objective and will not be/cannot be used to assess the primary endpoint, which is implant failure following IMRT. The data from the 10 patients in the experimental arm (Group 2A), however, will be used in the analysis of the primary endpoint since these 10 patients will have received IMRT.

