7.1 Voluntary Studies: Assessment of Cardiotoxicities and Quality of Life

Patients enrolled in this protocol are eligible to volunteer to be evaluated in one of the sub-studies below. Participation in these adjunct interventions is strictly voluntary and not required to assess the primary endpoint of the protocol, which is assessment of implant failure rates.

Given the large population of breast cancer patients who receive neoadjuvant chemotherapy for breast cancer and our departmental policy of pre-operatively evaluating such patients for radiation, the study plans to identify and recruit the patients needed for n=10 patients required for the —control group (Group 2B). Potential candidates will be identified at the time of pre-operative consultation in the radiation oncology department. It is customary for patients who have received neoadjuvant chemotherapy to be seen in a subsequent new visit following surgery, in order to discuss how response to chemotherapy impacts radiation treatment recommendations. At that time, if radiation therapy is not recommended, the patient will be offered enrollment onto the control arm (no RT) of the sub-study assessing early cardiotoxicity.

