7.1.2.1 Group 2A

Group 2A (n=10) are patients who will be receiving intensity-modulated radiation therapy to the (reconstructed) breast and regional lymph nodes. They will be approached regarding volunteering to receive the evaluations for assessment of cardiotoxicity and functional performance status outlined in Section 10.0. These evaluations will be performed 0-4 weeks prior to radiation therapy and 2-4 weeks after completion of radiation therapy.

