7.1.2.2 Group 2B

Group 2B (n=10) are patients who are receiving neoadjuvant chemotherapy and mastectomy, evaluated by Radiation Oncology for consideration of RT but do not receive RT. These 10 patients will serve as a control population against which to compare the effect of IMRT on early subclinical cardiotoxicity, and will be approached to receive the identical evaluations for assessment of cardiotoxicity as the 10 patients in the experimental group who do receive IMRT. The assessments for the control group will be performed at similar post-operative intervals as the experimental group: 4-8 weeks after surgery and at 15-20 weeks after surgery.

For breast cancer patients who receive neoadjuvant chemotherapy, it is customary for the Department of Radiation Oncology to preliminarily evaluate at a time point prior to the receipt of mastectomy. This allows adequate time for planning and sequencing of treatments, in the event that the patient opts for immediate reconstruction. After the mastectomy, the patient is seen for a second, subsequent new visit, at which time final pathology from the mastectomy is available to guide definitive treatment recommendations. We will plan to identify potential candidates for both the control and experimental arms at the first new visit prior to surgery and follow up with/enroll eligible volunteers at the second visit.

Patients in Groups 2A and 2B must meet the following inclusion criteria:

- a. Normal cardiac function (left ventricular ejection fraction $\geq 50\%$)
- b. Able to complete an acceptable baseline CPET, as determined by the absence of remarkable ECG findings or other inappropriate response to exercise
- c. Able to achieve an acceptable peak baseline CPET, as defined by any of the following criteria:

- i. achieving a plateau in oxygen consumption, concurrent with an increase in power output;
- ii. a respiratory exchange ratio ≥ 1.10 ;
- iii. attainment of maximal predicted heart rate (HR_{max}) (i.e within 10 bpm of age-predicted HR_{max} [$HR_{max}=220-Age(years)$]);
- iv. volitional exhaustion, as measured by a rating of perceived exertion (RPE) ≥ 18 on the BORG scale.

- d. Medical clearance from attending oncologist or attending radiation oncologist to undergo a symptom-limited cardiopulmonary exercise test.

Any of the following will exclude a patient from participating in Group 2A or 2B:

- a. Any of the following contraindications to cardiopulmonary exercise testing

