15.2 Randomization

There is no randomization.

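### Section 14.1.4 collects a baseline on every cardiotoxicity, fatigue and QoL measure but gives it no stated role in the non-randomised comparison of 10 IMRT and 10 control patients

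*Combined protocol and SAP*

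**What the plan says.** Section 14.1.4 opens with the baseline: "Each patient will provide baseline testing results after surgery and/or before the start of RT". It then plans a preliminary assessment, in 20 patients, of the association between IMRT receipt and CPET, strain echocardiography, blood markers, FMD and questionnaires, "using Wilcoxon rank sum test (for continuous measures) and Fisher exact test (for categorical measures". Of the 20 patients, "10 of them are in the control group of patients who do not receive IMRT (Group 2B". The section names no analysed variable (follow-up value or change), covariate or effect estimate. It also gives no alpha or power.

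For Group 2A, Section 7.1.2.1 says: "These evaluations will be performed 0-4 weeks prior to radiation therapy and 2-4 weeks after completion of radiation therapy". Section 7.1.2.2 places the Group 2B assessments at 4-8 and 15-20 weeks after surgery, and Section 16.1 labels the first assessment in each group as the baseline. The schedule tables in Section 10 mark all measures at both times.

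On how the groups arise, Section 15.2 says "There is no randomization". Section 7.1 explains that after the post-surgical visit, "if radiation therapy is not recommended, the patient will be offered enrollment onto the control arm (no RT". Section 7.1.2.2 gives the purpose of Group 2B: "These 10 patients will serve as a control population against which to compare the effect of IMRT on early subclinical cardiotoxicity".

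**The concern.** With 10 patients per group, the patient's own earlier value is the main source of precision available, and it is already being collected. It is also the only measured guard against reading a difference that existed before radiotherapy as an effect of radiotherapy. A two-sample rank-sum test with no stated variable and no covariate leaves open whether that guard is used.

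The silence matters for a second reason. The comparison covers several functional tests, two questionnaires and a panel of biomarkers (Section 3.2.2.4). If the analysed variable is not fixed in advance, follow-up or change could be chosen measure by measure after the data are seen.

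**Working it through.** **Plan's own figure.** Section 14.1.4 states no power or sample-size basis, so there is nothing to reproduce.

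**Inputs from the protocol.** 10 v 10, no randomisation, one baseline and one follow-up per patient, Wilcoxon rank-sum test.

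**Assumed inputs.** Two-sided alpha 0.05; SD 1; true effect 1.0 SD; baseline/follow-up correlation ρ from 0.3 to 0.9; normal data; no dropout.

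**Step 1: effective SD of each analysis.**
- Follow-up only: 1.
- Change: √(2(1−ρ)). This is below 1 only when ρ > 0.5.
- Baseline-adjusted: √(1−ρ²). This is below 1 for any non-zero ρ.

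**Step 2: normal-approximation power**, Φ(d/(SD·√(2/10)) − 1.96), with d = 1.
- Follow-up only: 1/0.447 = 2.236; 2.236 − 1.96 = 0.276; power 61%.
- Adjusted, ρ = 0.7: SD = √0.51 = 0.714; 2.236/0.714 = 3.131; 3.131 − 1.96 = 1.171; power 88%.
- Change, ρ = 0.3: SD = √1.4 = 1.183; 2.236/1.183 = 1.890; 1.890 − 1.96 = −0.070; power 47%.

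The approximation is optimistic at this size, so the tests themselves were simulated (20,000 replicates; exact rank-sum test, ANCOVA t-test for group).

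| ρ | Rank-sum, follow-up only | Rank-sum, change | ANCOVA |
|---|---|---|---|
| 0.3 | 51% | 39% | 58% |
| 0.5 | 52% | 52% | 67% |
| 0.7 | 51% | 73–74% | 82% |
| 0.8 | 51–52% | 89% | 92–93% |

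Rank ANCOVA gives about 56% to 87% over ρ = 0.3 to 0.8.

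Two qualifications apply:
- An unadjusted t-test already has 56% power here, so about 5 points of the ANCOVA gain (56 − 51) come from the parametric test and not from the baseline. At ρ = 0.3 only about 2 points (58 − 56) come from the baseline; at ρ = 0.7 about 26 points do (82 − 56).
- On skewed (lognormal) values at ρ = 0.3, untransformed ANCOVA falls to about 38%, against about 52% for the follow-up-only rank-sum test. Skewed biomarkers therefore need a transformation or ranks.

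**Step 3: carry-over of a baseline difference.** Assume a 0.5 SD difference at baseline, no IMRT effect, and ρ from 0.3 to 0.9.

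| Analysis | Difference acts through the baseline value | Difference persists fully |
|---|---|---|
| Follow-up only | bias 0.5ρ = 0.15 to 0.45 SD; rejects 5–14% | bias 0.5 SD; rejects about 16% |
| Change | bias −0.5(1−ρ) = −0.35 to −0.05 SD; rejects 9% to 5% | bias 0; rejects about 4% |
| ANCOVA | bias 0; rejects about 5% | bias 0.5(1−ρ) = 0.35 to 0.05 SD; rejects 12% to 6% |

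ANCOVA's false-positive rate is close to or below that of the follow-up-only test under both models. Neither ANCOVA nor change is unbiased under both.

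**Step 4: is 0.5 SD large for groups of this size?** Random allocation of 10 v 10 would give a chance baseline difference with SD √(2/10) = 0.447. P(|difference| > 0.5) = 2Φ(−0.5/0.447) = 2Φ(−1.118) = 26%.

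**The case against.** The strongest reply is that nothing in 14.1.4 says follow-up values alone are compared. The baseline is mentioned immediately before the test, and a rank-sum test applies equally well to change. Section 3.2.2.3 asks how far IMRT reduces cardiovascular reserve, and Section 16.1 pairs baseline with follow-up forms, so change is a natural reading. This stands: a reader might infer that the plan discards the baseline, but the documents show only that its role is unstated. Against the change reading, Section 14 mentions change where it is analysed elsewhere (Breast-Q scores in 14.1.2, flow and flow reserve in 14.1.3) and does not do so here.

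Second, a reader might infer that baseline differences are expected because the groups were not randomised. The documents do not show that. The radiotherapy decision is tied to chemotherapy response and pathology (Sections 7.1 and 7.1.2.2), not to cardiac function or fatigue. Section 9.4.1 describes all 20 patients as receiving neoadjuvant chemotherapy. Both groups need an LVEF of at least 50% and an acceptable baseline CPET. A difference is possible, and Step 4 shows that chance alone could produce a sizeable one, but the 0.5 SD used above is only an illustration.

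Third, preferring ANCOVA could be called taste: change rests on a different assumption and does better if a group difference simply persists. This stands in part, and is why change belongs in the plan as a sensitivity analysis. It does not justify leaving the choice open, and change is a poor sole remedy because it loses power at low correlation.

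**Conclusion.** The point holds as an unspecified analysis with a readily available improvement. It is not a demonstrated error. The size is conditional on follow-up values alone being compared: about 51% power against about 58% to 92% with ANCOVA for a 1 SD effect at correlations of 0.3 to 0.8, and carry-over of whatever group difference already existed. If change was intended, ANCOVA still has more power at every correlation tabulated, by a wide margin at 0.3 (58% v 39%) and a narrow one at 0.8.

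Effect size, alpha, correlations, normality and the imbalance are all assumptions, so the figures show direction and rough scale only. It would also be wrong to conclude that adjustment makes the groups comparable: one covariate does not remove confounding from selection by radiotherapy recommendation.

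Severity is low. The objective is exploratory, the assessment is described as preliminary, 20 volunteers are involved, no power is claimed and the primary endpoint is untouched.

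**What to change.** Amend Section 14.1.4 as follows:

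1. Name the analysed variable for each continuous measure as the follow-up value, and state that the baseline is the first of the two assessments.
2. Make the main comparison an ANCOVA of follow-up on group with baseline as covariate. For skewed biomarkers, use log-transformed values or rank ANCOVA, and list in advance which measures get which.
3. Report the adjusted group difference with a 95% CI where the scale allows.
4. Add the rank-sum test on change from baseline as a sensitivity analysis, not as a minimum substitute, and note that the two analyses rest on different assumptions about how a baseline difference evolves.
5. State that adjustment reduces but does not remove confounding from selection by radiotherapy recommendation.

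The cost is a change of wording and one degree of freedom per model. No visits, tests or patients are added.

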15.0 RESEARCH PARTICIPANT REGISTRATION AND RANDOMIZATION PROCEDURES

15.1 Research Participant Registration

Confirm eligibility as defined in the section entitled Criteria for Patient/Subject Eligibility.

Obtain informed consent, by following procedures defined in section entitled Informed Consent Procedures.

During the registration process registering individuals will be required to complete a protocol specific Eligibility Checklist.

All participants must be registered through the Protocol Participant Registration (PPR) Office at Memorial Sloan-Kettering Cancer Center. PPR is available Monday through Friday from 8:30am – 5:30pm at [contact]. Registrations must be submitted via the PPR Electronic Registration System (<http://ppr/>). The completed signature page of the written consent/RA or verbal script/RA, a completed Eligibility Checklist and other relevant documents must be uploaded via the PPR Electronic Registration System.

15.2 Randomization

There is no randomization.

16.0 DATA MANAGEMENT ISSUES

A Research Study Assistant (RSA) will be assigned to the study. The responsibilities of the RSA include project compliance, data collection, abstraction and entry, data reporting, regulatory monitoring, problem resolution and prioritization, and coordinating the activities of the protocol study team.

The data collected for this study will be entered into a secure database (Clinical Research Database—CRDB). Source documentation will be available to support the computerized patient record.

16.1 Data Collection

The following data forms (found in the regulatory binder) and appendices (found on ProtocolWeb) will be completed and entered into CRDB at specified time points according to the tables below:

Groups 1, 2, 2A:

Time Points:	Data Forms / Appendices:	To Be Completed By:
Baseline (Pre-Treatment)	• Minimal Data Set in CRDB (within 2 weeks of registration)	RSA
	• Data form 1: Patient Information	RSA
	• Appendix 3: Dose Parameters	Dosimetrist
3-10 Weeks Post-Exchange Surgery AND Follow-up	• Appendix 4a or 4b: Breast-Q Questionnaire	Patient
	• Dataform 3a: Evaluation of Capsular Contracture & Cosmesis by Radiation Oncologist	Radiation Oncologist
	• Dataform 3b: Evaluation of Capsular Contracture & Cosmesis by Plastic Surgeon	Plastic Surgeon
	• Data form 4: MRI Assessment	Radiologist

Groups 2A & 2B:

Time Points:	Data Forms / Appendices:	To Be Completed By:
Baseline: 0-4 Weeks Pre-RT (Group 2A) OR 4-8 Weeks Post-Mastectomy (Group 2B)	• Appendix 10: CPET Form	Exercise Physiologist
	• Appendix 11: CPET Recording Sheet	Exercise Physiologist
Follow-up: 2-4 Weeks Post-RT (Group 2A) OR 15-20 Weeks Post-Mastectomy (Group 2B)	• Appendix 12: FMD Form	Exercise Physiologist
	• FACIT and FACT-B Questionnaires	Patient

16.2 Quality Assurance

Regular registration reports will be generated to monitor patient accruals and completeness of registration data. Routine data quality reports will be generated to assess missing data and inconsistencies. Accrual rates and extent and accuracy of evaluations and follow-up will be monitored periodically throughout the study period and potential problems will be brought to the attention of the study team for discussion and action. Random-sample data quality and protocol compliance audits may be conducted by the study team, at a minimum of once per year, more frequently if indicated.

16.3 Data and Safety Monitoring

The Data and Safety Monitoring (DSM) Plans at MSKCC were approved by the NCI in September 2001. The plans address the new policies set forth by the NCI in the document entitled —Policy of the National Cancer Institute for Data and Safety Monitoring of Clinical TrialsII, which can be found at <http://cancertrials.nci.nih.gov/researchers/dsm/index.html>. The DSM Plans at MSKCC were established and are monitored by the Office of Clinical Research. The MSKCC DSM Plans can be found on the MSKCC Intranet at <http://mskweb2.mskcc.org/irb/index.htm>. There are several different mechanisms by which clinical trials are monitored for data, safety, and quality. There are institutional processes in place

for quality assurance (e.g. protocol monitoring, compliance and data verification audits, therapeutic response, and staff education on clinical research QA) and departmental procedures for quality control, plus there are two institutional committees that are responsible for monitoring the activities of our clinical trials programs. The committees: Data and Safety Monitoring Committee (DSMC) for Phase I and II clinical trials, and the Data and Safety Monitoring Board (DSMB) for Phase III clinical trials, report to the Center's Research Council and Institutional Review Board. During the protocol development and review process, each protocol will be assessed for its level of risk and degree of monitoring required. Every type of protocol (eg, NIH sponsored, in-house sponsored, industrial sponsored, NCI cooperative group, etc.) will be addressed and the monitoring procedures will be established at the time of protocol activation.

17.0 PROTECTION OF HUMAN SUBJECTS

Participation in this trial is voluntary. All patients will be required to sign a statement of informed consent, which must conform to IRB guidelines.

Inclusion of Women and Minorities: MSKCC has filed forms HHS 441 (civil rights), HHS (handicapped individual), 639-A (sex discrimination), and 680 (age discrimination); we also take due notice of the NIH policy concerning inclusion of women and minorities in clinical research populations. Only female patients will be accepted into the protocol. The proposed study population is as described in Section 6.0.

Exclusion of Lactating or Pregnant Women: Children have been excluded from this study. Thus, the relevance of this treatment to the pediatric population has not been established. Lactating and pregnant women are also excluded because of potential teratogenic effects of radiotherapy that may be harmful to the developing fetus or nursing infant.

Benefits: It is not known whether this treatment will affect the overall survival or local control of the patients.

Costs: The patient will be responsible for the costs of standard medical care including CT simulation. Patients will not be billed for the cost of the MRIs or $^{13}\text{N-NH}_3$ PET scans.

Incentives: No incentives will be offered to patients/subjects for participation in the study.

Confidentiality: Every effort will be made to maintain patient confidentiality. Research and hospital records are confidential. Patient's name or any other personally identifying information will not be used in reports or publications resulting from this study.

Incidental Clinically Significant Findings: Unlike clinical MRI exams, research images collected in this study may be of insufficient quality to yield any diagnostic information. Also, the investigational images are not immediately reviewed by radiologists. For these reasons, incidental findings may not be identifiable, or they may not be identified until long after the research MR exam is performed (in cases where the image production is delayed).

If an incidental clinically significant finding is detected on the research MRI sequences, the investigators and the PIs will propose an appropriate diagnostic imaging plan for such a finding. If a diagnostic MRI is already performed along with the research MRI, the incidental clinically significant finding will be

documented in the clinical MRI report and this will be communicated with the referring physician as per institutional guidelines. If the incidental clinically significant finding is detected only on the research MRI, such as in volunteers undergoing only research MRIs, then the finding and options for an appropriate diagnostic imaging plan will be discussed with the subject, and the discussion will be documented in our research file. In addition, the Institutional Review Board will be notified if this occurs.

17.1 Privacy

MSKCC's Privacy Office may allow the use and disclosure of protected health information pursuant to a completed and signed Research Authorization form. The use and disclosure of protected health information will be limited to the individuals described in the Research Authorization form. A Research Authorization form must be completed by the Principal Investigator and approved by the IRB and Privacy Board (IRB/PB).

17.2 Serious Adverse Event (SAE) Reporting

Any SAE must be reported to the IRB/PB as soon as possible but no later than 5 calendar days. The IRB/PB requires a Clinical Research Database (CRDB) SAE report be submitted electronically to the SAE Office at [contact]. The report should contain the following information:

Fields populated from CRDB:

- Subject's name (generate the report with only initials if it will be sent outside of MSKCC)
- Medical record number
- Disease/histology (if applicable)
- Protocol number and title

Data needing to be entered:

- The date the adverse event occurred
- The adverse event
- Relationship of the adverse event to the treatment (drug, device, or intervention)
- If the AE was expected
- The severity of the AE
- The intervention
- Detailed text that includes the following
 - A explanation of how the AE was handled
 - A description of the subject's condition
 - Indication if the subject remains on the study
 - If an amendment will need to be made to the protocol and/or consent form.

The PI's signature and the date it was signed are required on the completed report.

18.0 INFORMED CONSENT PROCEDURES

Before protocol-specified procedures are carried out, consenting professionals will explain full details of the protocol and study procedures as well as the risks involved to participants prior to their inclusion in

the study. Participants will also be informed that they are free to withdraw from the study at any time. All participants must sign an IRB/PB-approved consent form indicating their consent to participate. This consent form meets the requirements of the Code of Federal Regulations and the Institutional Review Board/Privacy Board of this Center. The consent form will include the following:

1. The nature and objectives, potential risks and benefits of the intended study.
2. The length of study and the likely follow-up required.
3. Alternatives to the proposed study. (This will include available standard and investigational therapies. In addition, patients will be offered an option of supportive care for therapeutic studies.)
4. The name of the investigator(s) responsible for the protocol.
5. The right of the participant to accept or refuse study interventions/interactions and to withdraw from participation at any time.
6. An option for eligible participants to indicate their voluntary participation in the PET/CT sub-cohort (thereby including this portion of the study in their overall written consent).

Before any protocol-specific procedures can be carried out, the consenting professional will fully explain the aspects of patient privacy concerning research specific information. In addition to signing the IRB Informed Consent, all patients must agree to the Research Authorization component of the informed consent form.

Each participant and consenting professional will sign the consent form. The participant must receive a copy of the signed informed consent form.

